### 8.2 SAMPLE SIZE DETERMINATION

Sample size is driven by Specific Aims 1 and 3 in the grant submission. In our previous study comparing 4 pedestrian training groups including the laboratory VR (Schwebel, McClure, et al., 2014a), we observed after 6 training sessions an adjusted mean change from post to pre of 280 milliseconds in start delay (after accounting for baseline value; field and VR trials averaged). To conclude the smartphone group is not inferior to the laboratory VR group with 80% power and type I error rate of 0.05, assuming a common SD of 0.50 (similar to that observed previously) and a non-inferiority margin of 0.12 (reflecting reduction in the gap before initiating crossing from post to pre of no less than 160 milliseconds, 50% of the more ecologically-valid field trial reduction of 320 milliseconds seen previously in VR group, and also the more conservative estimate between field vs lab assessment; Schwebel, McClure, et al., 2014a; 50% recommended by Mulla et al., 2012), we require a sample size of 216 per group (total N = 432) based on a two-sample test of difference in means. To account for attrition, estimated conservatively from our previous study's 9% attrition rate, we will inflate the sample size by 15%, recruiting a total N of 498.

We expect the hypotheses tested in Specific Aim 3 will be sufficiently powered also. Specific Aim 3 has two primary outcomes. For start delay, we expect sufficient power as: (a) the SD of start delay should be smaller than that for Specific Aim 1 given the larger number of training trials, and (b) as the SD decreases, the sample size required to declare noninferiority with the same margin will be smaller. For unsafe crossings, in the previous VR study we observed a mean of 0.20 (SD=0.20) for the follow-up mean percent of unsafe crossings. We assume that after additional training sessions, the mean percent of unsafe crossings will decrease and the variation will also decrease. With 216 per group, and assuming conservatively that the standard deviation decreases from 0.20 to 0.18, with alpha=0.025 and a non-inferiority margin of 5%, we have 82% power. In reality, we anticipate that the standard deviation will decrease further yet, which will result in increases in power for this hypothesis (SD=0.17 → power=86%; SD=0.16 → power=90%).

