### 8.3 STATISTICAL ANALYSES

Descriptive statistics for participants randomized to each intervention will be summarized for each outcome using standard measures of central tendency and variability. Several covariates may impact the relation between the intervention and the outcome measures of interest, including age, gender, temperament, attention during intervention, pedestrian experience, and verbal intelligence. Because children will be randomized to the interventions, we expect these covariates to be balanced across intervention groups. To test this, we will assess the relation between each covariate and intervention group. If differences emerge, those variables will be included as covariates in primary analyses. Primary inferential data analyses will address the study's three objectives. Specific Aim 1 is to test whether immersive training in the smartphone VR improves children's street-crossing skills after 6 training trials at a rate not inferior to improvement seen in the semi-immersive kiosk VR. Given its relevance especially during the early stages of learning pedestrian safety, start delay will serve as the primary dependent measure and the hypothesis of interest for testing change, assuming that an improvement is reflected by a negative value (that is, a lower post-training value is better), is:

$$H_0: \Delta_{LVR} - \Delta_{IVR} \geq \delta \text{ vs. } H_A: \Delta_{LVR} - \Delta_{IVR} < \delta$$

where  $\delta$  is the non-inferiority margin. We will perform ANCOVA to determine if the difference in change from post- to pre-intervention visits in the two groups falls below the non-inferiority margin, after adjustment for the baseline measure. If so, we will reject the null hypothesis and conclude training in the smartphone VR is not inferior to training in the kiosk VR. We will use similar methodology also to examine secondary outcome measures such as unsafe crossings and attention to traffic.

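### Coding improvement as negative conflicts with the printed non-inferiority hypothesis; taken together, they test whether the kiosk is non-inferior to the smartphone

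*Combined protocol and SAP*

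**What the plan says.** For Aim 1, section 8.3 proposes to "test whether immersive training in the smartphone VR improves" street-crossing skills at a rate not inferior to "improvement seen in the semi-immersive kiosk VR". Start delay is the primary measure. The text fixes the sign of change by "assuming that an improvement is reflected by a negative value (that is, a lower post-training value is better", and the displayed alternative hypothesis is "H_A: \Delta_{LVR} - \Delta_{IVR} < \delta". H0 is the complement, with the same difference at or above δ.

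The decision rule is an ANCOVA adjusted for baseline. H0 is rejected, and the smartphone called not inferior to the kiosk, if the "difference in change from post- to pre-intervention visits in the two groups falls below the non-inferiority margin".

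Section 8.2 gives the margin as 0.12 s, with an SD of 0.50 and 216 children per group, and has the same purpose: "To conclude the smartphone group is not inferior to the laboratory VR group". It cites an "adjusted mean change from post to pre of 280 milliseconds in start delay" from the earlier trial and relates the margin to a "reduction in the gap before initiating crossing from post to pre of no less than 160 milliseconds".

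Aim 3 (section 8.3) takes over the hypothesis, analyses and assumptions of Aim 1. It has two primary outcomes, start delay and unsafe crossings, each tested at post-intervention and at the 6-month follow-up.

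LVR, IVR and Δ are not defined in the text, and LVR and IVR are not in the abbreviation list (section 9.2).

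**The concern.** In a non-inferiority trial, the direction of the comparison is the test. The rule should make it hard to accept a smartphone platform that trains children less well than the kiosk. With improvement coded negative, a smartphone arm that learns less has a change closer to zero. Kiosk minus smartphone then becomes more negative and moves further below a positive margin. The worse the smartphone performs, the more readily it passes.

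This is the only formal statement of the confirmatory test. It governs the Aim 1 comparison and, through Aim 3, two outcomes at two time points: 1 + 2 × 2 = 5 comparisons. The prose makes the intent plain, but an analyst working from the section has to decide which of two conflicting statements to ignore.

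**Working it through.** **Labels.** Section 5.1.1 places the kiosk in a laboratory setting. Section 8.2 contrasts the smartphone group with the laboratory VR group. Section 8.3 calls the smartphone immersive and the kiosk semi-immersive. I therefore take LVR = kiosk and IVR = smartphone. This is an inference, because the document does not define the labels.

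**Inputs (section 8.2).**
- Start delay: SD 0.50, margin δ = 0.12 s, 216 per group, type I error 0.05, power 80%, earlier kiosk reduction 0.28 s.
- Unsafe crossings: SD 0.18, margin 0.05, alpha 0.025, 216 per group, power 82%.

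**Reproducing the plan's figures.**
- Start delay, one-sided 0.05, normal approximation: n = 2 × 0.50² × (1.645 + 0.842)² / 0.12² = 214.7 per group. With the t distribution, 80% power is first reached at 216.
- SE = 0.50 × √(2/216) = 0.0481. Power with equal arms = Φ(0.12/0.0481 − 1.645) = 80.2%. A one-sided 0.025 would give 70.3%, so I use one-sided 0.05 for start delay.
- Unsafe crossings: SE = 0.18 × √(2/216) = 0.0173. Power = Φ(0.05/0.0173 − 1.960) = 82.3%, matching the plan's 82%.

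**A single case.** Let Δ be post minus pre, so that improvement is negative. Suppose the kiosk changes by −0.28 s and the smartphone by 0.00 s (no learning). Then Δ_LVR − Δ_IVR = −0.28, far below +0.12, and H0 is rejected in favour of the smartphone.

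**Probability of declaring the smartphone non-inferior.** Let s be the smartphone's shortfall in improvement (s > 0 means smartphone worse). With improvement negative, Δ_LVR − Δ_IVR = −s. Hence:
- literal rule: P = Φ((δ + s)/SE − z)
- intended rule: P = Φ((δ − s)/SE − z)

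| Outcome | Shortfall s | Literal | Intended |
|---|---|---|---|
| Start delay | −0.12 s (smartphone better) | 5.0% | 99.96% |
| Start delay | 0 | 80.2% | 80.2% |
| Start delay | 0.06 s | 98.2% | 34.5% |
| Start delay | 0.12 s (at the margin) | 99.96% | 5.0% |
| Start delay | 0.28 s (no learning) | over 99.99% | under 0.01% |
| Unsafe crossings | 0 | 82.3% | 82.3% |
| Unsafe crossings | 0.05 (at the margin) | 99.99% | 2.5% |

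For example, at s = 0.12 the literal rule gives Φ(0.24/0.0481 − 1.645) = Φ(3.34) = 99.96%. A simulation of 4,000 trials per start-delay scenario agreed (99.95% literal and 4.7% intended at the margin).

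**Would a negative margin rescue the formula?** No. With δ = −0.12, rejection would require the kiosk to be better by more than 0.12 s. That happens with probability 95.4% when the smartphone gives no improvement and 0.002% when the arms are equal.

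**Where the slip may lie.** Section 8.2 treats reductions as positive quantities, and 0.28 − 0.16 = 0.12. If Δ is the reduction (pre minus post), kiosk minus smartphone below 0.12 is exactly the intended test. The printed formula would then be right and the sign sentence wrong.

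**The case against.** The strongest reply is that the formula is sound and one clause is loose. The decision rule in section 8.3 speaks of change from post to pre, which read literally is pre minus post, with improvement positive. Section 8.2 uses the same wording and gives positive figures, and its margin arithmetic fits. The remark that lower post-training values are better could describe the outcome rather than the coding of Δ. This is good evidence about which statement to correct, but the conflict remains: the text still says outright that improvement is a negative value, and the decision rule gives no order of subtraction between the arms.

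Second, the labels are inferred. If LVR were the smartphone, the formula would agree with the negative coding. That is true, and the labels may be defined in the grant submission or the published protocol that the document mentions. Within this document, all the wording points the other way.

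Third, the practical risk may be small. ANCOVA estimates the same adjusted contrast however the hypothesis is printed, and the aim, the conclusion sentence and the purpose of the sample size all name the intended direction. A careful analyst would probably notice. This stands, and it is why every error rate above is conditional on literal programming. It does not excuse a prespecified rule that contradicts itself on direction.

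**Conclusion.** The concern holds. With LVR as the kiosk and IVR as the smartphone, the sign sentence and the printed hypothesis in section 8.3 cannot both stand. Applied together with a positive margin, they test whether the kiosk is non-inferior to the smartphone. If programmed that way, the chance of accepting a smartphone that is worse by exactly the margin rises from 5% to 99.96% for start delay and from 2.5% to 99.99% for unsafe crossings. A smartphone better by 0.12 s would pass only 5% of the time.

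These figures rest on the plan's own SDs, margins and 216 per group, on one-sided 0.05 for start delay (the level that reproduces the planned size), and on the inferred labels. The document does not settle which of the two statements is the slip. The planned sample size and power are unaffected. Because this is the only formal decision rule for Aim 1 and Aim 3 inherits it, it must be corrected before analysis.

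**What to change.** Define LVR, IVR and Δ in section 8.3, then make one of these repairs, **not both**:

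- **Option A.** Keep improvement negative (Δ = post minus pre) and reverse the terms: H0: Δ_IVR − Δ_LVR ≥ δ versus HA: Δ_IVR − Δ_LVR < δ.
- **Option B.** Keep the printed formula and define Δ as pre minus post, so that improvement is positive. This matches the positive 280 ms and 160 ms in section 8.2.

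Making both repairs brings the fault back: Δ_IVR − Δ_LVR with improvement positive equals −s, which again gives 99.96% at the start-delay margin.

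State the order of subtraction in the ANCOVA sentence, for example: non-inferior if the upper one-sided confidence limit of the adjusted difference, taken in that order, lies below δ. Use the same convention for both Aim 3 outcomes, and state the favourable direction for each secondary outcome, since the sign must be reversed for any where higher is better.

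The cost is three definitions and one edit to either the sign sentence or the formula, plus the clarifying words on order and direction. Data, sample size and conduct stay as they are.

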## 1 PROTOCOL SUMMARY

### 1.1 SYNOPSIS

|   |  |
|---|--|
| Title:                             | Virtual Reality by Mobile Phone: Improving Child Pedestrian Safety   |
| Study Background:                  | Pedestrian injury is a serious public health concern for children in the United States and around the world. We have previously studied virtual reality as a mechanism to train children to be safer pedestrians. Virtual reality offers the opportunity for repeated practice at the complex cognitive-perceptual task of crossing a street, and we have demonstrated that it is effective to help 7- and 8-year-old children learn to cross streets more safely.   |
| Objectives:                        | This protocol extends previous work in two ways. First, we are unsure how much practice and training children need to achieve adult levels of pedestrian safety. We will offer children in this study up to 25 sessions of practice crossing the street in a virtual world to see when they achieve adult levels of safety. Second, we will evaluate whether training using a virtual reality program delivered to a mobile smartphone platform is as effective as training in a larger semi-immersive virtual pedestrian environment we have used previously. |
| Study Population:                  | 7 and 8 year old children  |
| Phase:                             | III  |
| Description of Study Intervention: | Pedestrian safety training in virtual reality  |

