### Training Protocol

Children will complete up to 25 training sessions. Training sessions will be scheduled about twice a week and will be identical in both groups except for the VR platform used. Children will engage in the VR for 3 sets of 15 crossings, or 45 crossings at each training session (expected duration ~30 minutes). The first two sets of crossings will be tailored to children's ability level, with traffic density set just beyond the level they previously succeeded crossing at. The third set of crossings will be standardized for all visits, at 30 MPH and 10 vehicles/minute/lane. Along with serving as a training trial, this third set will typically be a little easier for children, providing positive feedback and motivation for training. It also will offer a standardized assessment of ability.

All children will complete six visits to the laboratory for training. Following the sixth and all subsequent visits, we will monitor each child's number of unsafe crossings in the final standardized assessment.

When children complete two consecutive visits at a level equal to or safer than the average adult performance, they will be considered "competent" pedestrians functioning like an adult and training will be discontinued. Adult performance will be defined based on previous research with >300 adults.

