## 6 STUDY INTERVENTION DISCONTINUATION AND PARTICIPANT DISCONTINUATION/WITHDRAWAL

### 6.1 DISCONTINUATION OF STUDY INTERVENTION

Training will be discontinued after 25 sessions if children have not yet reached adult competency at that point. Training will be discontinued also if there is any sign of adverse or iatrogenic effect.

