### 6.3 LOST TO FOLLOW-UP

A participant will be considered lost to follow-up if they fail to attend multiple scheduled visits and/or are unable to be contacted by the study site staff.

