Specific Aim 2 is to (2a) demonstrate that most children achieve adult-level pedestrian functioning after 25 training sessions and (2b) demonstrate how many training sessions are sufficient to achieve this functioning. Because the safety of crossings is ultimately of greatest interest from a public health perspective, unsafe crossings will serve as the primary outcome for this aim; start delay will serve as a critical secondary outcome. Adult functioning will be estimated based on the performance of 311 healthy adults in four previous studies. Aim 2a will be evaluated via simple descriptive statistics to determine what percent of children achieve an unsafe crossings rate equivalent to adults in multiple simulated crossings. Aim 2b will also be evaluated descriptively, in this case by examining the average number of trials needed to achieve adult functioning across the sample, as well as the trajectory and distribution of that variable.

Specific Aim 3 is to test whether training in the smartphone VR improves children's street-crossing skills after 25 training trials, or fewer if adult functioning is achieved earlier, at a rate not inferior to improvement seen in the semi-immersive kiosk VR. Two dependent variables will be primary, start delay and unsafe crossings (other measures will be considered secondarily) and we will test the aim with the same hypothesis, analyses, and assumptions as in Specific Aim 1. Two sets of analyses will be conducted, one to test change from baseline to post-intervention and the second to test change from baseline to follow-up visits 6 months later.

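### Aim 2b averages sessions to adult level with no rule for children who never get there or leave early; Aim 3 plans no companion comparison of sessions by arm.

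*Combined protocol and SAP*

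**What the plan says.** The synopsis (1.1) states the question: up to 25 sessions of practice "in a virtual world to see when they achieve adult levels of safety". Section 8.3 answers it descriptively. Aim 2a gives the percentage of children who reach the adult unsafe-crossing rate, and expects this to be most of them. Aim 2b gives the mean number of trials (read here as sessions) to adult functioning over the whole sample, with its trajectory and distribution.

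Three rules determine whether a child has such a number:

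- Training Protocol (5.1.1): "When children complete two consecutive visits at a level equal to or safer than the average adult performance", training stops. Checking starts late: "Following the sixth and all subsequent visits, we will monitor" unsafe crossings in the standardised set.
- Section 6.1: "Training will be discontinued after 25 sessions if children have not yet reached adult competency at that point". Training also stops for any sign of an adverse or iatrogenic effect.
- Section 6.3: "A participant will be considered lost to follow-up if they fail to attend multiple scheduled visits" or cannot be contacted. Section 6.2 allows withdrawal.

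Aim 3 (8.3) tests the smartphone arm's improvement "after 25 training trials, or fewer if adult functioning is achieved earlier, at a rate not inferior to improvement seen" in the kiosk arm. It uses the Aim 1 ANCOVA of change, with start delay and unsafe crossings both primary. Number of sessions is not an outcome in 7.1 or 8.1, and no comparison of it between arms is specified.

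**The concern.** The Aim 2b average has no value for a child stopped at 25 sessions without competence, or for one who leaves before reaching it. Sections 6 and 8.3 give no value, exclusion or censoring rule. Two analysts could both follow the plan and report different answers to the synopsis question, and the usual shortcuts err towards too few sessions.

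The lesser issue is Aim 3. Unsafe crossings decide when a child stops and are also an Aim 3 primary outcome. A slower platform can therefore show up partly as more sessions and only partly as poorer final skill. The ANCOVA of change contains nothing about sessions, so on its own it supports a statement about skill at the end of training, not about rate. Without sessions by arm, a reader cannot tell whether similar final skill took similar training.

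**Working it through.** **Direction of the Aim 2b error.** Let T be the sessions a child would need. Entering 25 replaces T by min(T, 25), whose mean is below the mean of T whenever any child has T above 25. Averaging achievers only keeps just T of 25 or less, which is lower still. Neither statement needs a learning model. For early leavers, dropping them tends to favour quick learners; entering 25 for them could err either way.

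**Size of the Aim 2b error (assumed inputs).** The documents give neither the adult level nor learning curves. The assumed probability of an unsafe crossing at session t is 0.06 + 0.34·exp(−t/τ), with between-child spread (log-SD 0.4 in τ, SD 0.5 on the logit scale). There are 15 crossings in the standardised set. Training stops at the first two consecutive qualifying visits, from the pair 6 and 7 onward, with a cap of 25. Half speed means τ of 8 against 4. Arms are pooled, and the uncapped mean comes from running the model to 150 sessions.

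| Scenario | Adult level | Achievers only | 25 entered | Uncapped |
|---|---|---|---|---|
| τ 8 v 4 | 1/15 | 12.3 | 13.6 | 14.8 to 14.9 |
| τ 8 v 4 | 2/15 | 10.1 | 10.4 | 10.6 |
| τ 4 v 4 | 1/15 | 10.9 | 11.5 | 12.1 |

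- Row 1: 10% are not competent by 25, and 0.90 × 12.3 + 0.10 × 25 = 13.6. Shortfalls are 14.9 − 13.6 = 1.3 and 14.9 − 12.3 = 2.6.
- Row 2: the implied share not competent is (10.4 − 10.1)/(25 − 10.1), about 2%. Shortfalls are 0.2 and 0.5 on these rounded figures.
- Row 3: the implied share is (11.5 − 10.9)/(25 − 10.9), about 4%. Shortfalls are 0.6 and 1.2.

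With 15% also leaving early at random in row 1, 16% of children have no value. The Kaplan-Meier median stays at 12. The percent competent by 25 is 90%, or 84% if leavers count as not competent. If weaker children are three times as likely to leave, Kaplan-Meier gives 90.2% against a true 89.8%, with a bound of 83.1%.

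**Aim 3: the plan's own figure first.** Section 8.2 gives 82% power for unsafe crossings, "assuming conservatively that the standard deviation decreases from 0.20 to 0.18, with alpha=0.025 and a non-inferiority margin of 5" percent, with 216 per group. Power = Φ((0.05 − d)/SE − 1.96), with SE = SD·√(2/216). At SD 0.18, SE = 0.0173; at d = 0, 0.05/0.0173 − 1.96 = 0.93, so power is 82%. SDs of 0.17 and 0.16 give 86% and 90%, as stated.

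**The same formula for a half-speed smartphone arm.** Here d is the gap at each child's own stopping point.

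| Adult level | Gap (points) | Declared non-inferior, simulated SDs | SD 0.18 |
|---|---|---|---|
| 1/15 | 2.9 | about 71% | about 24% |
| 2/15 | 4.0 | about 18% | about 8% |
| 3/15 | 5.2 | 1–2% | 1–2% |

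These percentages move by a point or two between runs. At equal exposure the gap is about 8 points at six sessions, 5.8 at 12 and 2.0 at 25. A one-third-speed platform (12 v 4) at 1/15 has a gap of 5.1 and passes in about 2% of trials. If visits 5 and 6 may form the first pair, the gaps are 2.7, 3.8 and 5.0, so little changes.

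**Sessions by arm.** At 1/15 the half-speed arm uses 15.7 sessions against 11.5, a difference of 4.2. Since "Training sessions will be scheduled about twice a week", that is 4.2/2, about two weeks. With 249 per arm (498/2) and 15% leaving early, the difference in mean restricted to 25 sessions is 4.2, 2.9 and 1.8 at the three levels, with 95% half-widths of 1.0, 0.8 and 0.5. With equal platforms it is 0.0, and the interval excludes zero in 4–6% of trials.

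**The case against.** The strongest reply on Aim 2b is that it is descriptive, has no test, and already comes with the distribution and with Aim 2a's percentage. A reader would see that some children did not finish, and the error is small when nearly all do. This limits the harm, but a descriptive mean still needs a defined value for every child, and Aim 2a has no rule for early leavers either. It is also true that the uncapped mean extrapolates beyond the 25 sessions studied. That favours a median and a cumulative percentage, which do not extrapolate.

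On Aim 3, most of the reply stands. Training to competence is stated openly. Aim 1 compares the arms at an equal six sessions, on start delay as primary and unsafe crossings as secondary. Start delay does not trigger stopping, and a six-month analysis is planned. The formal conclusion in 8.3 speaks only of non-inferiority, so the rate wording is largely a matter of phrasing.

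A reader might go further and infer that the stopping rule masks an inferior platform. The documents do not support that. In the half-speed model the gap at stopping is smaller than at 12 sessions but larger than at a fixed 25, at all three adult levels. Only at the strictest level does the slow platform often pass, and the six-session gap of about 8 points exceeds the 5-point margin.

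**Conclusion.** The Aim 2b point holds: the planned average is right-censored without a handling rule. The direction of the error for children who reach the cap follows from the definition. Its size, about 1.3 to 2.6 sessions with 10% not competent and 0.6 or less with about 2%, rests wholly on assumed learning curves and adult levels.

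The Aim 3 point is secondary. Skill after training to competence is a legitimate target; what is missing is a comparison of the sessions each arm took to get there. No claim is made that the rule biases Aim 3 in a general direction, nor that a primary conclusion is unsafe. The change should be made, but the trial does not depend on it.

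**What to change.** Leave the training rule as it is and amend 8.3.

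1. **Aim 2b.** Replace the plain average with the discrete-time Kaplan-Meier median and the cumulative percent competent by session, overall and by arm, censored at 25 sessions or last visit. State which of the two qualifying visits is the event and that censoring is assumed non-informative. Show a bound that counts early leavers as not competent. Include in it children whose training stops for adverse effects, since such stops could differ by platform.
2. **Beside Aim 3.** Report sessions to competence by arm as a supportive, non-gating analysis: the difference in mean restricted to 25 sessions, with a confidence interval. Label it as capped at 25, not as the sessions ultimately needed; without dropout the restricted mean equals the mean with 25 entered. Word the Aim 3 conclusion as skill at the end of training.

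The cost is SAP wording and a little more analysis of data already collected. Training, sample size, margins and alpha do not change. The downside is a narrower Aim 3 conclusion.
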